8.2.9.2.3. Cardiac Laboratory Abnormalities

In addition to routine ECG monitoring in all treatment arms, additional monitoring for potential cardiac toxicity is included for subjects treated with CC-122. This includes routine monitoring of troponin-T and BNP as well as more intensive monitoring of ECGs and LVEF as described in Section 6. Elevations of troponin-T or BNP warrant further investigation including assessment of the subject for signs and symptoms of cardiac injury, consideration of a cardiology consultation, other cardiac evaluations (such as an exercise stress test, additional evaluation of LVEF, or other cardiac tests recommended by a cardiologist), and the addition of cardioprotective therapy (eg, beta blockers) as appropriate. Laboratory evaluation to assess for assay interference may also be warranted. Isolated asymptomatic elevations of troponin-T or BNP without associated ECG or LVEF changes or other cardiac findings do not require that

CC-122 dose be held. For any elevation of troponin-T > ULN associated with either significant elevation of BNP (20% increase from baseline with an absolute value > 100 pg/mL) or associated cardiac symptoms or findings, CC-122 dosing should be held and the sponsor should be notified. Additional cardiac monitoring should be performed as described in [Table 14](#) and as medically indicated. CC-122 may be restarted at the same dose or a reduced dose, in consultation with the sponsor, based on troponin-T/BNP guidelines in [Table 14](#) and general guidelines provided in Section 6.

8.2.9.2.4. Pneumonitis

Pneumonitis has been observed in patients taking CC-122. The diagnosis should be considered in subjects presenting with non-specific respiratory signs and symptoms such as hypoxia, pleural effusion, cough, dyspnea, or interstitial pulmonary infiltrates, and in whom infectious, neoplastic and other causes are excluded by appropriate investigations. Subjects should be specifically advised to report promptly any new or worsening respiratory symptoms they experience.

Those with radiological features suggestive of non-infectious pneumonitis but with minimal (Grade 1) symptoms may continue CC-122 without dose alteration. For drug-related Grade 2 pneumonitis, CC-122 treatment should be interrupted and corticosteroids may be indicated. Once symptoms have resolved completely, CC-122 may be reintroduced at the next lower dose level. For drug-related Grade 3 or 4 pneumonitis CC-122 must be permanently discontinued and corticosteroids are recommended until clinical symptoms have resolved.

8.2.10. Management of Select AEs While Receiving Obinutuzumab

8.2.10.1. Infusion-Related Reactions (IRRs)

Two-thirds of patients experienced IRRs with the first infusion of obinutuzumab; reactions can also occur with subsequent infusions, but the frequency is lower ([GAZYVA](#), [GAZYVARO](#)). Infusion reactions typically occur within 24 hours of receiving obinutuzumab. Symptoms may include anaphylaxis, acute life-threatening respiratory symptoms, hypotension, tachycardia, dyspnea, bronchospasms, larynx and throat irritation, wheezing, and laryngeal edema. Additional potential symptoms include nausea, vomiting, diarrhea, hypertension, flushing, skin rash, urticaria, headache, pyrexia, and chills.

To minimize the potential for these reactions, premedication is administered as described in Section 9.3.3. Full emergency resuscitation facilities should be immediately available in the event of a severe and life-threatening infusion reaction and subjects should be under close supervision of the investigator or appropriately trained staff during the infusions. Medical

management of infusion reactions should be instituted according to standard medical practice using glucocorticoids, epinephrine, oxygen, intravenous fluids and other medications as medically indicated. Subsequent infusions should be administered with appropriate premedications as in Section 9.3.3.

Subjects with pre-existing cardiac or pulmonary conditions should be monitored more frequently throughout the infusion and after the infusion. Hypotension may occur and investigators should consider withholding antihypertensive agents (for subjects not at risk for hypertensive crisis) for 12 hours prior to, during the infusion, and for 1 hour after the infusion until blood pressure is stable.

8.2.10.2. Progressive Multifocal Leukoencephalopathy

John Cunningham (JC) virus infection resulting in progressive multifocal leukoencephalopathy (PML), which can be fatal, has been observed in patients treated with obinutuzumab. Subjects with new onset or changes to pre-existing neurologic manifestations should be evaluated for PML. The symptoms of PML are unspecific and can vary depending on the affected region of the brain. Motor symptoms with corticospinal tract findings (eg, muscular weakness, paralysis, and sensory disturbances), sensory abnormalities, cerebellar symptoms, and visual field defects are common. Some signs/symptoms regarded as “cortical” (eg, aphasia or visual-spatial disorientation) may occur. Evaluation of PML includes, but is not limited to, consultation with a neurologist, brain MRI, and lumbar puncture [REDACTED]

[REDACTED] Obinutuzumab and CC-122 should be discontinued in subjects who develop PML. The subject should be referred to a neurologist for the evaluation and treatment of PML.

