8.2.9.1. General Dose Modification Guidelines

Subjects will be evaluated for AEs at each visit with the NCI CTCAE (version 4.03) used as a guide for the grading of severity, with the exception of tumor flare (NCI CTCAE version 3.0), [REDACTED] and laboratory abnormalities as recommended by the IWCLL guidelines for the diagnosis and treatment of chronic lymphocytic leukemia [REDACTED] as listed below:

Subjects experiencing related AEs or SAEs \geq Grade 3 must interrupt dosing of the responsible IP or both IPs until resolution of the toxicity to \leq Grade 1 or baseline severity unless as otherwise indicated in [Table 14](#). If IP-related events do not resolve to \leq Grade 1 or baseline severity within 28 days despite adequate medical management, the sponsor's study medical monitor should be notified.

The dose of CC-122 may be reduced successively by one level from the starting dose. There will be no more than one dose level reduction from one cycle to the next unless otherwise permitted after consultation with the sponsor medical monitor. In addition, if a subject continues to experience unacceptable toxicity after two dose reductions (with the exception of CC-122 per [Table 15](#) where up to 3 dose reductions may be allowed for selected doses), IP will be discontinued permanently. If a dose is reduced for toxicity other than a Grade 4 non-hematological toxicity, re-escalation is permitted after the toxicity is resolved. If the toxicity recurs after re-escalation, the subject should remain at the lower dose level. Subjects who experience a Grade 4 non-hematological toxicity may not have their dose re-escalated.

For the combination of CC-122 and ibrutinib or obinutuzumab, in the event of a toxicity requiring dose modification, CC-122 should be considered for interruption and dose reduction first if possible. If the subject continues to require dose modification after a dose hold and/or reduction of CC-122 a dose interruption of obinutuzumab or ibrutinib or reduction of ibrutinib may be considered.

Dose interruptions lasting beyond 28 days should be discussed with the sponsor's study medical monitor.

If it becomes necessary to permanently stop administration of one of the IPs, continuation on the other IP will require discussion and agreement between the sponsor's study medical monitor and the investigator.

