8.2.9.2. Dose Modification Guidelines

Any IP-related toxicity meeting the definition of DLT will require dose reduction or interruption. The criteria for dose reduction are listed in [Table 14](#), should be used for dose modifications.

Chronic Grade 2 toxicity (other than specified below) may warrant dose reduction or interruption of one or both IP. Such cases should be discussed with the sponsor's medical monitor before changes are made.

Dose modification decisions for patients with cytopenia (below the lower limit of the normal range) at **baseline** will be based on the IWCLL guideline ([Table 13](#)). For patients with a normal neutrophil count, platelet count and/or hemoglobin value at baseline, the NCI CTCAE (version 4.03) will be used.

Any dose modifications must be recorded on the respective Study Drug Record eCRF.

Table 14: Dose Reduction Guidelines

Adverse Event	Grade	Action	Agent to be considered for interruption/reduction (in descending order)
Thrombocytopenia	≥ Grade 3	
• Hold all IP• Follow CBC at least every 7 days• If thrombocytopenia resolves to ≤ Grade 2, restart IP and reduce CC-122 to the next lower dose level. Ibrutinib may be restarted after thrombocytopenia resolves to ≤ Grade 1 or baseline at original dose after the 1st occurrence, and reduce by one dose level at each subsequent recurrence with a maximum of 2 dose reductions allowed. A 4th recurrence requires permanent discontinuation of ibrutinib.• Obinutuzumab should be restarted at the full dose after thrombocytopenia resolves to ≤ Grade 2, no dose reduction is allowed.	
• CC-122• Ibrutinib/obinutuzumab

Table 14: Dose Reduction Guidelines (Continued)

Adverse Event	Grade	Action	Agent to be considered for interruption/reduction (in descending order)

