Surgical Procedures	Minor	
 Hold one or more IPs at investigator's discretion on day of surgery IPs may be restarted at same dose level upon recovery 	
 Ibrutinib CC-122
	Major	
 Hold one or more IPs for 3 to 7 days prior to surgery through 3 to 7 days post surgery Restart IPs upon recovery and at least 3 to 7 days post surgery at the same dose level 	
Infusion Reaction	Grade 1-2	
 Reduce infusion rate ($\leq 50\%$ prior rate) or interrupt infusion and treat symptoms Upon resolution, continue or resume infusion; infusion rate increments and intervals may resume at the increments and intervals as appropriate for the treatment dose if no further infusion reaction symptoms 	
 Obinutuzumab
	Grade 3 (severe) infusion reaction	
 Interrupt infusion and manage symptoms Upon resolution, restart infusion at $\leq 50\%$ prior rate; infusion rate escalations can resume at the increments and intervals as appropriate for the treatment dose if no further infusion reaction symptoms Permanently discontinue if Grade 3 or higher infusion-related symptom occurs with re-challenge 	
	Grade 4 (life threatening) infusion reaction	
 Stop infusion immediately; permanently discontinue 	

Table 14: Dose Reduction Guidelines (Continued)

Adverse Event	Grade	Action	Agent to be considered for interruption/reduction (in descending order)
Progressive Multifocal Leukoencephalopathy	All	
 Permanently discontinue 	
 Obinutuzumab
Pneumonitis	Grade 2	
 Hold one or more IPs at investigator's discretion Once symptoms have resolved completely, CC-122 and/or ibrutinib may be restarted at the next lower dose level. 	
 CC-122 Ibrutinib
	≥ Grade 3	
 Discontinue one or more suspected IPs permanently 	

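### For PML, Protocol Section 8.2.10.2 stops obinutuzumab and CC-122 but the Table 14 row lists obinutuzumab only, and neither says clearly what applies once obinutuzumab is complete

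*Protocol*

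**What the plan says.** Two places in the protocol deal with PML.

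- Section 8.2.10.2, in the part on managing selected events under obinutuzumab, describes PML as potentially fatal and states: "Obinutuzumab and CC-122 should be discontinued in subjects who develop PML".
- Table 14 in Section 8.2.9.2 has a row labelled "Progressive Multifocal Leukoencephalopathy", covering all grades. Its action is "Permanently discontinue" and its agent column contains one entry, "Obinutuzumab".

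Section 8.2.9.2 says that the criteria in Table 14 "should be used for dose modifications". No text says whether the table or the narrative section prevails when they differ.

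Section 8.2.9.1 adds a general rule. If one investigational product has to be stopped permanently, "continuation on the other IP will require discussion and agreement between the sponsor's study medical monitor and the investigator". Section 8.2.12.3 refers back to Section 8.2.9.1 for obinutuzumab dose modification.

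On timing, Sections 4.1 and 8.2.2.3 end obinutuzumab at Cycle 6 and allow CC-122 for at most 24 cycles. The SAP contains no rule on PML.

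**The concern.** A site that consults the table finds one drug to stop. A site that reads Section 8.2.10.2 finds two. The drug on which they differ is CC-122, the study drug, which may continue long after obinutuzumab has ended.

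What is at stake is subject safety and uniform conduct across sites, not an estimate or a test. Amendment 7 closed enrollment but was issued to guide the care of subjects still on treatment, so the instruction remains live for any Arm C subject still receiving CC-122. It could also reach Arm A subjects who added obinutuzumab after progression, as Section 4.1 permits.

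**Working it through.** The plan gives no figure to reproduce on this point. The check is a comparison of the passages.

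1. **Agent lists for the same event.** Section 8.2.10.2: obinutuzumab and CC-122. Table 14, PML row: obinutuzumab. The lists differ by CC-122. The table also makes the stop permanent, while Section 8.2.10.2 does not use that word.

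2. **Is the missing entry an artefact of the text?** It does not look like one. The row is legible and has no redaction. Other rows name several agents where several are meant: the allergic reaction row lists obinutuzumab, CC-122 and ibrutinib, and the pneumonitis row lists CC-122 and ibrutinib. The redaction in Section 8.2.10.2 comes before the stopping sentence, which is complete.

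3. **Would a reader of the table be led to the fuller text?** Not by the row itself. The troponin row refers the reader to Section 8.2.9.2.3, but the PML row has no pointer to Section 8.2.10.2.

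4. **While both drugs are being given (through Cycle 6).** A site acting on the table permanently stops obinutuzumab. Section 8.2.9.1 then applies, and CC-122 can continue only with the agreement of the medical monitor and the investigator. Continuation is not automatic, but it is permitted, whereas Section 8.2.10.2 says CC-122 should be discontinued. The difference is narrowed, not removed.

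5. **After Cycle 6, with CC-122 alone.** Three things change.
   - The table row names a drug that is no longer being given, so it has nothing to act on.
   - The agreement rule is conditioned on a need to stop one of the products permanently. Where obinutuzumab has simply been completed, that condition may not be met.
   - The heading of Section 8.2.10 confines that section to events under obinutuzumab treatment. A site could reasonably read Section 8.2.10.2 as still in force or as lapsed.

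6. **How long this second period can last.** By study cycle the ceiling is 24 − 6 = 18 cycles, Cycles 7 to 24. It is approximate, because CC-122 starts on Cycle 1 Day 9. Sections 4.1 and 8.2.2.3 also mention 3 further CC-122 cycles for subjects who pass 24. This is a maximum and does not measure expected exposure.

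**The case against.** The strongest reply is that this is an incomplete table row and not a pair of opposing instructions. Table 14 never says to continue CC-122 after PML; it is silent. Section 8.2.10.2 is specific to the event and explicit, so a site that follows both stops both drugs and breaks neither. The table concerns dose reduction, and its agent column is headed as a list of drugs to consider for interruption or reduction, which hardly overrides an explicit stop elsewhere. Section 8.2.9.1 gives further protection: a related event of Grade 3 or worse calls for holding the responsible drug or both, unless Table 14 provides otherwise, and CC-122 is the first drug considered when a combination needs modification.

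Much of this stands. A reader might infer that the protocol leaves a subject with PML on CC-122 by default. The documents do not support that, because Section 8.2.9.1 requires agreement while both drugs are in use. A reader might also infer that the conflict spans all CC-122 treatment, or 18 of 24 cycles for a typical subject. That is not supported either. The heading of Section 8.2.10 makes the overlap clear only while obinutuzumab is given, and 24 cycles is an upper limit that progression, toxicity or other discontinuation can shorten.

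Some of the reply does not stand. The reconciling reading depends on the site finding Section 8.2.10.2 unprompted. The Grade 3 rule covers only related events, asks for interruption until recovery, and gives way to Table 14. None of it settles what applies after obinutuzumab is complete.

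**Conclusion.** The inconsistency is real, and it is one of internal consistency, not of trial design. For PML the protocol gives two agent lists, sends sites to the shorter one, and does not say which governs. Through Cycle 6 the practical consequence is limited by the agreement rule, though that rule permits what Section 8.2.10.2 says should not happen. After Cycle 6 the gap is wider, because none of the three provisions clearly applies to a subject on CC-122 alone.

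The size cannot be put as a number of subjects. The documents do not say how many Arm C subjects remain or how many cycles they have received, and the legible text gives no incidence for PML. I assume that few subjects, possibly none, would be affected. The point rests on the seriousness that the protocol itself assigns to the event and on the ease of correction. It has no bearing on sample size or on any planned analysis. It should be corrected, and nothing here says which clinical rule is the right one.

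**What to change.** Reconcile the Table 14 PML row with Section 8.2.10.2 so that both list the same agents and both state whether the stop is permanent. Add a pointer from the row to that section. State whether the rule applies after obinutuzumab has been completed, and whether it covers Arm A subjects who added obinutuzumab. Notify sites with ongoing subjects. The choice of rule belongs to the sponsor's clinical and safety staff.

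The cost is a protocol clarification letter. No change to the design, sample size or SAP is needed.

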8.2.10.3. Neutropenia, Thrombocytopenia, and Anemia

[REDACTED]

Severe and life-threatening thrombocytopenia, including acute thrombocytopenia (occurring within 24 hours after the infusion), has been observed during treatment with obinutuzumab. Fatal hemorrhagic events have also been reported in Cycle 1 in patients treated with obinutuzumab (GAZYVA, GAZYVARO). A clear relationship between thrombocytopenia and hemorrhagic events has not been established. Subjects should be closely monitored for thrombocytopenia, especially during the first cycle. Regular laboratory tests should be performed until the event resolves, and dose delays should be considered in case of severe or life-threatening thrombocytopenia. Transfusion of blood products (ie, platelet transfusion) according to institutional practice is at the discretion of the treating physician. Use of all concomitant therapies, which could possibly worsen thrombocytopenia-related events such as platelet inhibitors and anticoagulants, should also be taken into consideration, especially during the first cycle.

Hematopoietic growth factors or other hematologic support, such as erythropoietin, darbepoetin, granulocyte-colony stimulating factor (G-CSF), granulocyte-macrophage colony stimulating factor (GM-CSF), RBC- or platelet- transfusions are allowed in the study with therapeutic intent.

Therapeutic use of G-CSF is allowed at any time for subjects experiencing Grade 3 or 4 neutropenia or any grade febrile neutropenia. Prophylactic use of granulocyte (or granulocyte-macrophage) growth factors is not allowed during Cycle 1.

8.2.10.4. Gastrointestinal (GI) Perforation

Cases of gastrointestinal perforation have been reported in patients receiving obinutuzumab (**GAZYVA**, **GAZYVARO**) mainly in NHL. Monitor patients with GI involvement for GI perforation.

8.2.11. Management of Select AEs While Receiving Ibrutinib

Fatal bleeding events have occurred in patients treated with ibrutinib (**IMBRUVICA**). Grade 3 or higher bleeding events (subdural hematoma, gastrointestinal bleeding, hematuria and post procedural hemorrhage) have occurred in up to 6% of patients. Bleeding events of any grade, including bruising and petechiae, occurred in approximately half of patients treated with **IMBRUVICA**. The mechanism for the bleeding events is not well understood. **IMBRUVICA** may increase the risk of hemorrhage in patients receiving antiplatelet or anticoagulant therapies.

Consider the benefit-risk of withholding **IMBRUVICA** for at least 3 to 7 days pre and post-surgery depending upon the type of surgery and the risk of bleeding.

Inform subjects of the possibility of bleeding, and report any signs or symptoms (blood in stools or urine, prolonged or uncontrolled bleeding). Inform the subject that **IMBRUVICA** may need to be interrupted for medical or dental procedures.

Subjects should be closely monitored for hemorrhagic events. Regular laboratory tests should be performed until the event resolves, and dose delays should be considered in the event of \geq Grade 2 hemorrhage (**Table 14**). Transfusion of blood products (ie, RBC- or platelet- transfusions) according to institutional practice is at the discretion of the treating physician.

For any subjects receiving ibrutinib (Arm B), major hemorrhages as defined in Section 11.1 are considered adverse events of special interest and must be reported on the Serious Adverse Event Report Form using the “Important Medical Event” as the seriousness criteria and sent via email or fax to Celgene and/or designee, within 24 hours of awareness (see Section 11.5.1).

8.2.11.1. Interstitial Lung Disease (ILD)

Cases of ILD have been reported in patients treated with ibrutinib. Monitor patients for pulmonary symptoms indicative of ILD. Should symptoms develop, follow the protocol dose modification guidelines as outlined in **Table 16**.

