8.2.2.2. Arm B: CC-122 in Combination with Ibrutinib

Subjects in Arm B will be administered CC-122 orally on a 5/7-day schedule. CC-122 will be initiated on Cycle 2 Day 1 and on Day 1 of each cycle thereafter up to a maximum of 24 cycles of CC-122, or until disease progression, unacceptable toxicity or discontinuation for any other reason, whichever is earlier. Each dose will be taken in the

morning with about 8 ounces of water. CC-122 may be taken up to 12 hours late if dosing has been delayed on a single day; otherwise that day's dose should be omitted.

Dosing of ibrutinib is as described in the [IMBRUVICA](#) package insert or SmPC. Subjects will take orally three 140 mg capsules of ibrutinib daily for a total daily dose of 420 mg. Ibrutinib should be taken once daily at approximately the same time each day. The capsules should be swallowed whole with water and subjects should not open, break or chew capsules. Ibrutinib will be administered daily starting Cycle 1 Day 1 up to a maximum of 24 cycles of CC-122, or until disease progression, unacceptable toxicity or discontinuation for any other reason, whichever is earlier. For patients who discontinue CC-122 prior to 24 cycles or if patients have surpassed the 24 cycles of CC-122, Celgene will continue to provide an additional 3 cycles of ibrutinib from the investigational supply to allow time for patients to be transitioned to commercially available ibrutinib and/or other therapies at the discretion of the treating physician. Toxicity-related dose interruptions and modifications for ibrutinib are described in Section [8.2.12.2](#).

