8.2.12. Dose Reduction Steps

If a subject develops toxicity, the dose of CC-122 may be reduced as outlined in **Table 15** and ibrutinib as outlined in **Table 16**.

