8.2.12.2. Ibrutinib Dose Reduction Steps

Ibrutinib dose reduction steps are shown in [Table 16](#).

Table 16: Ibrutinib Dose Reduction Steps

Non-Hematologic Adverse Events	
Toxicity Occurrence	Action to be Taken
First	Withhold ibrutinib until recovery to Grade \leq 1 or baseline; may restart at original dose level, 420 mg daily
Second	Withhold ibrutinib until recovery to Grade \leq 1 or baseline; may restart at 1 dose level lower, 280 mg daily
Third	Withhold ibrutinib until recovery to Grade \leq 1 or baseline; may restart at 1 dose level lower, 140 mg daily
Fourth	Discontinue Ibrutinib

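### The ILD instruction for ibrutinib points only to Table 16, which permits a full-dose restart, and not to the stricter Pneumonitis row of Table 14

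*Protocol*

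**What the plan says.** Protocol Section 8.2.11.1 is the only ibrutinib instruction in the visible text that is specific to ILD. It asks sites to watch for pulmonary symptoms and then says: "Should symptoms develop, follow the protocol dose modification guidelines as outlined in" Table 16. It does not mention Table 14.

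Table 16 (Section 8.2.12.2), as shown, covers non-hematologic events by occurrence number only. After a first event, ibrutinib is withheld until Grade 1 or lower, or baseline, and then "may restart at original dose level, 420 mg daily". The second and third occurrences allow 280 mg and 140 mg, and the drug is stopped at the fourth.

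Table 14 (Section 8.2.9.2) has a Pneumonitis row that lists CC-122 and ibrutinib as the agents. At Grade 2 the investigator chooses which drug or drugs to hold, and then: "Once symptoms have resolved completely, CC-122 and/or ibrutinib may be restarted at the next lower dose level". At Grade 3 or higher the action is: "Discontinue one or more suspected IPs permanently".

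Section 8.2.9.2.4 describes pneumonitis as presenting with non-specific respiratory signs "such as hypoxia, pleural effusion, cough, dyspnea, or interstitial pulmonary infiltrates". Its dose rules address CC-122 alone, for example: "For drug-related Grade 3 or 4 pneumonitis CC-122 must be permanently discontinued".

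The general ibrutinib pointers also lead to Table 16. Section 8.2.2.2 says "Toxicity-related dose interruptions and modifications for ibrutinib are described in Section" 8.2.12.2. The sentence in Section 8.2.12 that begins "If a subject develops toxicity, the dose of CC-122 may be reduced as outlined in" Table 15 goes on to name Table 16 for ibrutinib.

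**The concern.** The instruction written for this particular event names the more permissive of two tables. An investigator with an ibrutinib subject who develops dyspnea and interstitial infiltrates would reasonably turn to the ILD subsection, and from there be sent to a table that ignores severity. The row that does separate Grade 2 from Grade 3 and above is not cited there.

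At stake is rechallenge with ibrutinib at 420 mg after severe lung toxicity, in a situation where another part of the same protocol calls for permanent discontinuation of the suspected drug. Enrollment is closed, but the instruction still governs Arm B subjects continuing on ibrutinib and any Arm A subject who adds ibrutinib after progression (Section 4.1).

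**Working it through.** The plan states no figure to reproduce, so the check is a comparison of text with two lines of arithmetic.

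**Step 1. Can one subject fall under both instructions?** Section 8.2.9.2.4 lists interstitial infiltrates among the signs of pneumonitis, and the Table 14 Pneumonitis row lists ibrutinib as well as CC-122. The two can overlap clinically. The protocol does not say that they are the same event.

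**Step 2. First event in a subject taking ibrutinib 420 mg.**

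| Severity | Table 16 (cited by 8.2.11.1) | Table 14 Pneumonitis row |
|---|---|---|
| Grade 1 | Occurrence-based steps, no grade split | No entry |
| Grade 2, ibrutinib is the drug held | Restart permitted at 420 mg once at Grade 1 or lower, or baseline | Restart only after complete resolution, at the next lower level: 280 mg |
| Grade 3 or higher, ibrutinib is the suspected drug | Restart permitted at 420 mg once at Grade 1 or lower, or baseline | Permanent discontinuation |

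**Step 3. Size.**
- Grade 2, ibrutinib held: 420 − 280 = 140 mg/day; 420 / 280 = 1.50. The permitted restart dose is 50% higher under Table 16 and can begin before symptoms have fully cleared.
- Grade 3 or higher, ibrutinib suspected: Table 14 allows 0 restarts. Table 16 permits one at 420 mg after the first event. It permits up to 3 in all (420, 280 and 140 mg), but reaching 3 takes three separate events.

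**Step 4. Is the stricter row deliberate?** The Table 14 rows for liver tests, for stomatitis/nausea/vomiting/constipation and for diarrhea all write out the 420, 280, 140 mg sequence, which matches Table 16. The Pneumonitis row does not. It has its own recovery threshold, restart dose and stopping rule. The parent section, 8.2.11, sends ibrutinib-related hemorrhage to Table 14. This pattern suggests that the Table 16 citation for ILD is a misdirected cross-reference.

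**Step 5. Does another section settle it?**
- Section 8.2.9.1 defers to Table 14, but that clause concerns related events of Grade 3 or higher and so does not reach Grade 2.
- Section 8.2.9.2 makes Table 14 the general source for dose modification. It does not say what happens when an event-specific sentence names a different table.
- Section 8.2.9.2.4 gives actions for CC-122 only.

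None of the three clearly overrides the ILD sentence.

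**The case against.** The strongest reply is that a full reading already leads to Table 14. Section 8.2.11.1 does not say that Table 16 replaces it. Sections 8.2.9.1 and 8.2.9.2 both send the reader there, and Table 16 only permits a restart, so a site can satisfy both tables by not restarting. That stands as a description of what a careful investigator could do. It does not remove the problem, because the sentence a site would look up for this event names the other table and no rule of precedence is stated.

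Second, Table 14 leaves room for judgment. At Grade 2 the investigator may hold one or more drugs, and Section 8.2.9.1 asks that CC-122 be considered for interruption and reduction first if possible. Holding CC-122 alone and leaving ibrutinib at 420 mg would comply. A reader might infer that Table 14 always requires 280 mg at Grade 2. It does not: the contrast applies only when ibrutinib is the drug held. At Grade 3 or higher the row refers to one or more suspected drugs, so with both drugs suspected it does not plainly require stopping ibrutinib. The contrast is clearest when ibrutinib is the suspected drug, which is the case 8.2.11.1 is written for.

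Third, treating ILD and pneumonitis as overlapping is an inference. Section 8.2.9.2.4 introduces pneumonitis as an effect seen with CC-122 and requires other causes to be excluded. The SAP item in Section 11.1.1, Interstitial Pneumonitis, is only the name of a MedDRA query. The inference is clinically reasonable, but it should be stated as one.

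Finally, a reader might extend the point to other Table 14 rows stricter than Table 16: tumor lysis, venous thrombosis, rash and confirmed Hy's Law. The documents do not support that. No event-specific sentence sends those events to Table 16 alone, and a full reading resolves them in favor of Table 14.

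**Conclusion.** The cross-reference in Section 8.2.11.1 is wrong as written and should be corrected. Following it permits full-dose ibrutinib after a first ILD event of any grade once the event has recovered. The Table 14 Pneumonitis row is stricter in two situations: Grade 2 with ibrutinib held, and Grade 3 or higher with ibrutinib suspected.

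The conclusion rests on three assumptions: that ILD on ibrutinib would often also meet the protocol's description of pneumonitis; that ibrutinib is the drug held or suspected; and that nothing in Sections 8.2.9.2.1 and 8.2.9.2.2, which are not visible in the public copy, settles the matter.

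The documents give no ILD frequency, so no effect at arm level can be stated. A reader might infer that the dose-finding results are affected. Nothing here supports that: the point concerns the safety of subjects continuing on ibrutinib, and no DLT, MTD or efficacy conclusion changes.

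**What to change.** In Section 8.2.11.1, replace the sole reference to Table 16 with wording to this effect: *follow the Table 14 Pneumonitis row for events of Grade 2 or higher, with permanent discontinuation of ibrutinib if it is suspected at Grade 3 or higher; use Table 16 only for the size of the ibrutinib dose step and for events that row does not cover (Grade 1).*

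Keeping Table 16 for Grade 1 matters, because the Pneumonitis row has no Grade 1 entry and the Grade 1 advice in Section 8.2.9.2.4 is for CC-122 only. The parenthesis also settles the case in which both drugs are suspected, which the row leaves open.

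No other section needs to change. A general rule ranking Table 14 over Table 16 is not needed for this point. Because this is a dosing instruction, the cost is a small protocol amendment with IRB/EC approval under Section 14.5. The SAP is unaffected.
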